2. OBJECTIVE(S)

2.1. Primary Objective

To determine the proportion of patients with chronic ITP who do not respond to 75 mg of eltrombopag daily given for at least 3 weeks but then do respond to eltrombopag given daily first for 2 weeks at doses of 100, then for 2 weeks at 125 mg and finally for 4 weeks at a dose of 150mg daily. The intial double-blind phase will stop if/when the platelet count exceeds 100,000/uL. Complete response (CR) will be defined as 2 consecutive platelet counts of greater than or equal to 50,000 AND an increase of greater than or equal to 20,000 from the study baseline within the 8 week increased dose window not as a result of rescue treatment. Partial response (PR) will be defined as 2 consecutive platelet counts of greater than or equal to 50,000 OR an increase of greater than or equal to 20,000 from the study baseline within the 8 week increased dose window not as a result of rescue treatment.

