The trial will have an 80% statistical power at the 5% level of significance (two sided) to detect a difference in the proportion of subjects receiving increased dose of eltrombopag with a primary response (2 consecutive platelet counts of > 50,000 and an increase of > 20,000 from the study baseline with in the 8 week increased dose window not as a result of rescue treatment) to subjects without a primary response in the placebo group assuming 50% of subjects randomized to active drug will have a response and 5% of subjects randomized to placebo would have a response. The same statistical test will be run for subjects who achieve partial response. An interim analysis was performed after 18 subjects to test for futility and efficacy.

Dose modification during the long term extension portion of the trial will be made on the basis of individual platelet response to a maximal dose of 150mg. All subjects can be monitored at 4 weeks intervals and then can go to every 8 weeks for the remainder of the study at the discretion of the investigator (investigator may require subjects to come in for additional monitoring if deemed necessary).

If the platelet count is > 150,000 ul and < 400,000 ul the daily dose will be adjusted and if > 400,000 ul the medication will be held and monitor will be as per the prescribing information for eltrombopag in the package insert. However, if the P-I determines that adjusting the subject's dose will negatively affect the subject, he or

she may decide not to escalate or reduce the subject's dose. Circumstances in which this may occur include, but are not limited to: investigator is tapering other medications or the subject has a viral infection. Viral infections have been known to both increase and decrease platelet count in patients with ITP. It is suggested that the increased presence of inflammatory molecules during a viral infection increases platelet production, causing platelet count to increase. Alternatively, platelet count may decrease by virtue of activating the reticuloendothelial system causing greater phagocytosis of antibody-coated platelets and/or platelet production.

Laboratory/Assessment Testing

Please see Appendix 1 for Schedule of Events.

Screening

CBC with Differential
Reticulocyte Count
Peripheral Smear
CMP (Sodium, Potassium, Bicarbonate, Chloride, BUN, Creatinine, Glucose, Calcium, Total Protein, Albumin, including AST/ALT, Fractionated Bilirubin Level)
Urine Pregnancy Test (when appropriate)

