5. STUDY TREATMENTS

5.1. Treatment Assignment

Subjects will be randomly allocated in a two to one ratio to receive treatment or placebo. Subjects and investigators will be blinded to randomization. Randomization will be stratified according to splenectomy status. Randomization will be performed at the time of informed consent with a computer generated randomization table

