8.2. Study Design Considerations

8.2.1. Sample Size Assumptions

The trial will have a 80% statistical power at the 5% level of significance (two sided) to detect a difference in the proportion of patient receiving increased dose of eltrombopag with a primary response (Platelet Count $\geq 50,000$ per cubic millimetre and $> 20,000$ above baseline) to patients without a primary response in the placebo group. assuming 50% of patients randomized to active drug will have a response and 5% of patients

randomized to placebo would have a response. An interim analysis will be performed after 18 subjects to test for futility and efficacy and also to re-estimate sample size. If neither futility nor efficacy are met the trial would continue to enroll. Based on the observed treatment effect at the interim analysis the sample size would be allowed to expand to up to 60 subjects

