8.3. Data Analysis Considerations

8.3.1. Key Elements of Analysis Plan

The analysis would primarily be descriptive except for the primary endpoint. In order to make the study feasible, the current plan for 36 patients does not allow for much flexibility. It does allow for a confirmatory study from the patients on placebo who can then follow the 8 weeks of dose escalation treatment as an open label study (note they will have been on 75 mg of eltrombopag for at least 11 weeks at that time). All secondary analyses will be underpowered but will be descriptive.

Analysis of efficacy will be based on the intention to treat population of all subjects who underwent randomization.

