8.3.1.1. Interim analysis

Results of Interim analysis:

In the interim analysis of 18 subjects, the data suggests that non-splenectomized patients tended to have greater average platelet counts compared to splenectomized patients for the first 8 weeks in the open-label extension phase. When subjects were on active drug, the results revealed that males tended to have a higher complete response rate compared to females.

Of note, three subjects were removed due to SAEs, however only one patient was removed because of a study drug related event (elevated LFTs). Further analysis will be performed after 36 patients and 60 patients are enrolled to evaluate the long term efficacy and safety of eltrombopag at doses higher than 75 mg.

Primary Response Criteria:

Complete Response (CR) will be defined as a 2 consecutive platelet counts $\geq 50,000 / \mu\text{L}$ AND $> 20,000$ more than the baseline platelet count at enrollment within the 8 week increased dose window not as a result of rescue treatment. Partial Response (PR) will be defined as a 2 consecutive platelet counts $\geq 50,000 / \mu\text{L}$ OR $> 20,000$ more than the baseline platelet count at enrollment within the 8 week increased dose window not as a result of rescue treatment. Odds of response will be analyzed using logistical regression for binary response variables.

Secondary Response Criteria:

- Platelet Count \geq 50,000 and $>$ 20,000 above baseline for at least 3 of the last 4 of 8 weeks independent of rescue therapy
- Platelet Count \geq 50,000 /uL and $>$ 20,000 above baseline for any 4 of 8 weeks independent of rescue therapy
- At least One Platelet count \geq 100,000
- Number of weeks with Platelet Counts \geq 50,000 /uL and $>$ 20 from baseline in 8 Weeks reduction of bleeding score from baseline to the last count of the study improvement of HRQoL
- Number of weeks with Platelet Counts $>$ 100,000 in 8 Weeks

Secondary Efficacy Endpoints:

- Dose required achieving first platelet count \geq 50,000 /uL ?and $>$ 20 from baseline
- Average Platelet Count at each dose level
- Bleeding scores using Page score and WHO score
- Use of Rescue Treatment

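### The status of partial response is inconsistent: it gets the same significance test as complete response, under primary headings, with no order or alpha split

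*Combined protocol and SAP*

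**What the plan says.** Section 2.1 (Primary Objective) defines both responses. CR needs two consecutive counts of at least 50,000 and a rise of at least 20,000. The other reads: "Partial response (PR) will be defined as 2 consecutive platelet counts of greater than or equal to 50,000 OR an increase". Sections 6.3 and 8.3.1.1 list both again as primary response criteria, and 8.3.1.1 adds: "Odds of response will be analyzed using logistical regression for binary response variables". It does not say whether the p-value is Wald, likelihood-ratio, exact or penalised.

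Section 8.2.1 sets the level: "The trial will have a 80% statistical power at the 5% level of significance (two sided) to detect a difference". The response used there, and in the matching paragraph of 3.1, is the AND definition. Section 3.1 then says of the other endpoint: "The same statistical test will be run for subjects who achieve partial response".

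Other places point to CR alone. Section 3.1 twice describes the primary endpoint, in the singular, by the AND rule, and the hypothesis in 8.1 uses the same rule. Section 8.3.1 says "The analysis would primarily be descriptive except for the primary endpoint" and makes all secondary analyses descriptive. No section gives an order of testing, a split of the 5%, or a rule for the case where CR misses and PR is significant.

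**The concern.** The stated 5% covers one test. If PR is a second inferential test with equal standing, an ineffective dose increase has two chances of a significant result on something labelled a primary response. If PR is not primary, 8.3.1 makes it descriptive, and that conflicts with the significance test in 3.1 and with PR's place in 2.1, 6.3 and 8.3.1.1. The plan needs the same edit on either reading. At stake is what the sponsor may claim if the two endpoints disagree.

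**Working it through.** **Inputs from the documents.** Two-sided 5% and 80% power (8.2.1). Rates: "assuming 50% of subjects randomized to active drug will have a response and 5% of subjects randomized to placebo would have a response" (3.1). Allocation: "Subjects will be randomly allocated in a two to one ratio to receive treatment or placebo" (5.1). Size: "the current plan for 36 patients does not allow for much flexibility" (8.3.1), so 24 active and 12 placebo. Sections 4.1 and 8.2.1 allow 60, so 40 and 20.

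**Inputs assumed.** The documents give only the 5% placebo rate, for CR. I take null rates of 5-10% for CR and 15-25% for PR, equal in both arms. PR includes CR, as the OR wording implies. There are no covariates and the 2:1 split is exact. The interim looks are a separate matter and are left out.

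**The plan's own figure.** With a pooled rate of (0.05 + 2 × 0.50)/3 = 0.35, the placebo arm needs

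n = [1.96 √(0.35 × 0.65 × 1.5) + 0.8416 √(0.05 × 0.95 + 0.5 × 0.5/2)]² / 0.45² = (1.145 + 0.350)² / 0.2025 ≈ 11.03.

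That rounds up to 12 placebo and 24 active, total 36. The plan's figure is reproduced, for one test on CR.

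**Large-sample reference for two tests.** Independent tests would give 1 − 0.95² = 9.75%. CR is nested in PR, so the tests are correlated, with ρ = √[p_CR(1 − p_PR) / (p_PR(1 − p_CR))]. At 5% and 15% this is √(0.0425/0.1425) = 0.55, and the either-test rate is 8.9%.

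**Exact small-sample rates.** Each arm is a trinomial (CR, PR only, neither) with the same probabilities in both arms. I sum the probability of every pair of outcomes with two-sided p ≤ 0.05 on CR, on PR, or on at least one. Wald results with a zero cell count as non-significant.

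One setting in full (N=60, CR 5%, PR 15%):

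| Test | CR alone | PR alone | Either |
|---|---|---|---|
| Likelihood-ratio | 5.6% | 6.3% | 10.9% |
| Pearson | 4.0% | 4.4% | 7.8% |
| Fisher | 1.5% | 3.4% | 4.6% |
| Wald | 0.5% | 2.4% | 2.8% |

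Range over CR 5-10%, PR 15-25%, N=36 and 60:

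| Test | CR alone | Either |
|---|---|---|
| Likelihood-ratio | 3.9-7.4% | 9.8-11.6% |
| Pearson | 3.6-4.0% | 6.0-8.5% |
| Fisher | 0.7-2.8% | 2.6-5.7% |
| Wald | 0.1-1.8% | 1.5-5.0% |

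These rates count both directions, as the plan's two-sided level does. If PR meant PR without CR, the picture is similar: at N=36 with CR at 5%, likelihood-ratio gives 7.6-10.4% and Wald 0.2-4.1% over assumed total response rates (CR plus PR-only) of 10-45%.

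**Why Wald is low.** With a 5% placebo rate, the chance of no placebo responder is 0.95¹² = 54% at N=36 and 0.95²⁰ = 36% at N=60, and Wald then cannot reject. The same sparseness cuts its power for CR at the planned rates to about 29% at N=36 and 62% at N=60. Fisher keeps 81.5% at N=36.

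**Effect of ordering.** If PR is tested only after CR is significant, the either-test rate under no effect equals the CR-alone column. At N=60 that still leaves 5.6-7.4% with the likelihood-ratio test, so the order alone does not restore 5%. Splitting alpha instead (2.5% each) replaces 1.96 by 2.24: (1.309 + 0.350)²/0.2025 ≈ 13.6, so 14 + 28 = 42 patients.

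**The case against.** The strongest reply is that CR is plainly the intended primary endpoint. The hypothesis, the power statement and every singular mention of the primary endpoint use the AND definition, and 8.3.1 speaks of one primary endpoint. This stands. A reader might infer that the plan declares CR and PR co-primary, but the documents do not go that far. They contradict themselves on PR. The reply does not remove the point, because PR keeps its primary headings and its significance test.

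A reader might also infer that the planned logistic regression doubles the false-positive rate. The documents do not support that, since they name the model but not the test. Near 10% arises with the likelihood-ratio test. With Wald from the same model, the either-test rate does not exceed 5% in the settings above. Part of the likelihood-ratio excess is that test's own small-sample error, visible in CR alone at N=60. In the other direction, Wald and Fisher stay near or below 5% because they are conservative with sparse cells, and the plan does not choose either.

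Finally, PR being easier to reach does not by itself raise the error. Fluctuation affects both randomised arms alike, and the added error comes from the second test.

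**Conclusion.** The point holds as an inconsistency with a real but test-dependent effect on error. PR's standing is undefined, and following the text as written permits a significance claim on a primary criterion after CR has missed. Under all four tests, adding PR raises the chance of a false positive above that for CR alone. The either-test rate runs from about 1.5% to 11.6%, and whether it passes 5% turns on the unnamed test. These figures rest on the assumed null rates, on no covariate adjustment and on PR including CR. The documents support neither a declared co-primary design nor a fixed doubling of the 5%. The matter affects how the main result may be claimed and does not invalidate the trial.

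**What to change.** - State in 2.1, 3.1 and 8.3.1 that CR is the single primary endpoint.
- Test PR at two-sided 5% only if CR is significant at two-sided 5%. Otherwise report PR as an estimate with a confidence interval and no significance claim.
- Move PR to the secondary endpoints in 2.1, 6.3 and 8.3.1.1, and exempt this one ordered test from the descriptive rule in 8.3.1.
- Name the test and choose one that holds its level with sparse cells, for example an exact test. Fisher's CR-alone error is 0.7-2.8% in the settings above, and its 81.5% power at N=36 still meets the stated 80%.
- Date the change and record that it follows the existing hypothesis and sizing, because 8.3.1.1 already reports interim response results and subjects are unblinded after Part 1.

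The cost is the loss of a stand-alone PR claim when CR misses. The sample size stays as planned, and the ordering takes no power from CR. Splitting alpha equally would keep a separate PR claim but would raise 36 to 42, or lower approximate power at 36 from 84% to 73%.

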1.2. Rationale

It therefore seems possible, even likely, that in ITP patients who did not respond at a dose of 75mg daily, eltrombopag could be more effective at a higher dose. Therefore, we would like to explore doses as high as 150 mg po daily in order to see if we can demonstrate efficacy in those patients unresponsive to 75 mg daily. We propose a double blind randomized controlled trial in ITP patients who have been defined as 'non-responders' at the maximum dose (75mg) of eltrombopag. The study will also assess efficacy and toxicity at higher daily doses (100mg, 125mg, 150mg) in this population. The study will be performed at a single center in North America, (Weill Cornell Medical College). There will be two parts to it. First the randomized double blind part to be described next. Subsequently an open label study similar to the EXTEND study (TRA105325;<https://www.clinicaltrials.gov/ct2/show/NCT01880047?term=[name]+Dose+Escalation&rank=1>) in patients who responded at doses of 100 to 150mg to see if they maintain or even improve their response and to investigate the eltrombopag safety profile over up to 18 months at these higher doses.

Furthermore, the patients randomized to the placebo arm can go on open label treatment at higher doses if they did not increase their counts on placebo. Even though open label, they will serve as a confirmatory group.

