Dose escalation will continue, despite satisfaction of the primary endpoint of study ($> 50,000$ and $> 20,000$ above baseline), until the platelet count reaches 100,000. The rationale for this approach is to maximize clinically relevant responses for the subjects and standardize data for analysis. Subjects will stop study medication if the platelet count is within the normal range, thereby minimizing any safety risk associated with elevated platelet count. By continuing to dose escalate subjects until the platelet count is $> 100,000$, the maximum response and correlation of dose will be tracked allowing better understanding of sustained response and dose-dependent response, which can be applied to future consideration dosage for periods of short-term hemostasis (i.e surgical procedures). The 8 weeks of data collected in enrolled subjects on the standardized

protocol will have the balance of consistency of dosage and unequivocality of response while maintaining subject safety.

If agreed on by the P-I, subjects may obtain local counts or see their local hematologist for study visits. All study-required procedures will be faxed to the P-I for review. The appropriate dosing adjustments will be determined by the P-I.

According to the new consensus guidelines (Provan Blood, 2009), male and female subjects with > 1 year duration of ITP are diagnosed with chronic ITP. Enrollment began with adult subjects \geq 18 years of age, and was extended to include pediatric patients $>$ 12 years of age after a review of this unblinded safety information by the independent Data Safety Monitoring Officer (DSMO). Additionally, we will now allow the inclusion of pediatric patients \geq 3 year of age to enroll on the protocol. The rationale for treating patients on this study is to allow people to be successfully treated and thus increase their platelet count by using a higher dose of eltrombopag when they do not respond to 75 mg daily of eltrombopag. Since some children do not respond to 75mg, the rationale and the dosing (when and how to increase) would be the same.

Long Term Treatment Extension (Part 2): (48 months)

After 8 weeks or once dosing is stopped because the platelet count is $>100,000$, the subject will be unblinded, once the data forms are complete with the assistance of the research pharmacy.

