At Enrollment: (Part 1)

CBC with Differential
Reticulocyte Count
Peripheral Smear
CMP (Sodium, Potassium, Bicarbonate, Chloride, BUN, Creatinine, Glucose, Calcium, Total Protein, Albumin, including AST/ALT, Fractionated Bilirubin Level)
Platelet Reticulocyte Count
Eye Examination for caratacts
History, Physical with Vital Signs and Bleeding Score
HRQOL

Every 2 Weeks until week 8:

Reticulocyte count, Platelet Reticulocyte count
Peripheral Smear (if indicated)
CMP
History, Physical with Vital Signs and Bleeding Score

Long Term Treatment Extension: (Part 2)

Performed at each study visit:

CBC with Differential platelet count, Reticulocyte count, Platelet Reticulocyte count
Peripheral Smear (if indicated)
History, Physical with Vital Signs

After the end of treatment during the dose escalation phase, all subjects can be monitored at 4 weeks intervals and then can go to every 8 weeks for the remainder of the study at the discretion of the investigator (investigator may require subjects to come in for additional monitoring if deemed necessary).

After 6 months on therapy:

Eye Examination

After 12 months on therapy:

Bone Marrow Aspirate and Biopsy
HRQOL

After 18 months on therapy:

Eye Examination

After 24 months on therapy

Bone Marrow Aspirate and Biopsy

*Please Note: A bone marrow aspiration/biopsy will only be performed at 24 months if the subject's reticulin fibrosis grade is a 2 or 3 during the 12 month procedure.
HRQOL

After 36 Months on therapy

Bone Marrow Aspirate and Biopsy

*Please Note: A bone marrow aspiration/biopsy will only be performed at 36 months if the subject's reticulin fibrosis grade is a 2 or 3 during the 24 month procedure.

HRQOL

After 48 Months on therapy

Bone Marrow Aspirate and Biopsy

*Please Note: A bone marrow aspiration/biopsy will only be performed at 48 months if the subject's reticulin fibrosis grade is a 2 or 3 during the 36 month procedure.

HRQOL

Post Study Period after completion of dosing

Weekly

CBC with Differential platelet count, Reticulocyte count, Platelet Reticulocyte count
Peripheral Smear (if indicated)

History, Physical with Vital Signs and Bleeding Score
HRQOL (Week 1 – End of 8 Week Blinded study/ End of Extension Study)

Every 2 Weeks until week 4:
CMP
History, Physical with Vital Signs and Bleeding Score

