6.4.6.1. Regulatory reporting requirements for SAEs

The PI and/or data coordinator will be reporting unexpected serious adverse events promptly to the IRB, FDA and to Novartis within appropriate regulatory timeframe.

We will be reporting:

- WCMC IRB as per WCMC AE Reporting Policy
- FDA as per Safety Reporting Requirements for IND and BA/BE (21CFR312.32)
- Novartis will be informed of all SAE within 24 hours
- WCMC Data Safety Monitoring Board

6.4.6.2 Data Safety Monitoring Plan:

We will be utilizing the Weill Cornell Medical College Data Safety Monitoring Board (DSMB) to review the IRB-approved protocol, informed consent forms and safety reports. The DSMB will review data semi-annually to evaluate the safety, efficacy, and compliance with all local IRB, FDA and ICH regulations/requirements for this study. Adverse events and unanticipated problems will be submitted to the DSMB semi-annually. A Grade 4 or above adverse event will result in an immediate submission of a periodic report to the DSMB. All serious adverse events will be immediately submitted to Novartis and to the FDA under the IND.

The Principal Investigator will submit all written DSMB recommendations at the time of the continuing review. Individual recommendations will be submitted upon receipt of review comments.

Safety Evaluation

This protocol is investigator initiated. The Principal Investigator is responsible for the study and will monitor the safety of the patients on the protocol.

The following safety will be reviewed by the Principal Investigator:

- Physical Exam
- Vital Signs
- Laboratory results (blood count, liver function tests, reticulocyte count)
- SAE and AE events
- Bone marrow aspirations/biopsies (if relevant)

Early Stopping Rules

Individual Stopping Rules

- Adverse event that would in the investigators judgment, make continued participation in the study an unacceptable risk
- Development or diagnosis of new thrombotic event

- Development of new-onset, clinically-significant, ocular changes related to cataracts on serial ophthalmology examinations
- Development of MF3 fibrosis on bone marrow examinations
- Development of Drug Induced Liver Injury

Liver chemistry stopping criteria and follow up requirements have been implemented to assure subject safety and evaluate liver event etiology in alignment with the FDA Guidance for Industry – Drug-Induced Liver Injury: Premarketing Clinical Evaluation.

Liver chemistry stopping criteria 1-5 are defined as follows:

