Dose modification during the long term extension portion of the trial will be made on the basis of individual platelet response to as high a dose as 150mg. If the platelet count is > 150,000 ul and < 400,00 ul the daily dose will be adjusted and if > 400,000 ul the medication will be held and monitor will be as per the prescribing information for eltrombopag in the package insert. However, if the P-I determines that adjusting or stopping the subject's dose will negatively affect the subject, he or she may decide not to escalate, reduce, or stop the subject's dose. Circumstances in which this may occur include, but are not limited to: investigator is tapering other medications or the subject has a viral infection. Viral infections have been known to both increase and decrease platelet count in patients with ITP. It is suggested that the increased presence of inflammatory molecules during a viral infection increases platelet production, causing platelet count to increase. Alternatively, platelet count may decrease by virtue of activating the reticuloendothelial system causing greater phagocytosis of antibody-coated platelets and/or platelet production.

Data Collection and Monitoring

Data will be collected and entered into a Microsoft excel eCRF by the clinical research coordinator. Data will be entered into the eCRF after each study visit. The Principal investigator will verify the data quarterly to ensure that the data collected and entered is accurate.

Interim Analysis:

An interim analysis was performed after 18 patients were enrolled in the study. The data suggested that non-splenectomized patients tended to have higher average platelet counts compared to splenectomized patients for the first 8 weeks in the open-label extension phase. When subjects were on active drug, the results revealed that males tended to have a higher complete response rate compared to females. Of note, three subjects were removed due to SAEs, however only one patient was removed because of a study drug related event (elevated LFTs). Further analysis will be performed to evaluate the long term efficacy and safety of Eltrombopag at doses higher than 75 mg after 36 and then 60 patients have completed 8 weeks of active medication.

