8.3.1.2. Safety Analyses

For safety analysis the population for analysis will include all randomized subjects who received at least one dose of study medication. Subjects will be evaluated according to the treatment they received.

Malignancy

Malignancy will be descriptive

Bone Marrow Reticulin Fibrosis

Bone Marrow Fibrosis monitoring will involve performing bone marrow aspirate and biopsy on any consenting patient who elects to remains enrolled in long term extension after 12 months of therapy. All marrows will be read by Drs [name] and [name] at Weill-Cornell Medical Center.

Re-occurrence of thrombocytopenia

Re-occurrence of thrombocytopenia will be defined as platelet count $<$ 10,000 uL or 10,000 ul decrease from baseline platelet count at enrollment in the 4 weeks following discontinuation of the study medication

Thrombosis

Thrombosis will be descriptive

Drug Induced Liver Injury

Elevations in ALT > 3 time upper limit of normal or bilirubin level > 2 times the upper limit of normal will be monitored and assessed for continuation or stopping of study drug as per Phase II Liver Safety Algorithm (see Appendix)

Incidence of new and progression of previously identified cataracts

Cataract assessment will involve a baseline eye exam in all enrolled patients with subsequent evaluations at 6 months and 18 months in the patients that continue to receive therapy in the long term extension study. If possible re scheduling, all exams will be performed by [name].

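### Routine liver chemistry has no stated timing in Part 2, although the liver stopping criteria and safety review depend on it there

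*Combined protocol and SAP*

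**What the plan says.** Under Laboratory/Assessment Testing, Section 3.1 gives the tests "Performed at each study visit" of the extension. The laboratory entry is "CBC with Differential platelet count, Reticulocyte count, Platelet Reticulocyte count", followed by a smear if indicated and by history, physical examination and vital signs. CMP is not in the list, and none of the entries at 6, 12, 18, 24, 36 and 48 months adds it.

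ALT and bilirubin come from the CMP, which Section 3.1 describes at screening and enrolment as containing "Albumin, including AST/ALT, Fractionated Bilirubin Level". The same section names CMP for screening, enrolment, the two-weekly Part 1 visits and the post-study period.

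Other parts of the protocol count on liver tests without limiting them to Part 1:

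- The Safety Evaluation in Section 6.4.6.2 has the investigator review "Laboratory results (blood count, liver function tests, reticulocyte count").
- Section 8.3.1.2 says that ALT or bilirubin elevations "will be monitored and assessed for continuation or stopping of study drug as per Phase II Liver Safety Algorithm".
- Sections 6.4.1 and 6.4.6.2 define five liver stopping criteria tied to study treatment, and Section 4.4 makes drug-induced liver injury a ground for withdrawal.
- Appendix 1 has a CMP row in its Part 2 table, with no time point marked.

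On duration, Section 3.1 has the heading "Long Term Treatment Extension (Part 2): (48 months"), whereas Section 1.2 describes studying safety "over up to 18 months at these higher doses".

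**The concern.** Part 2 is where exposure to doses of up to 150 mg is longest, and Section 1.2 gives the safety profile at these doses as one of its purposes. Section 6.4 names hepatotoxicity as a known risk and reports liver test abnormalities in 11% of eltrombopag patients against 7% on placebo in the earlier controlled studies. A stopping rule based on a laboratory value works as intended only if that value is measured on a known schedule. A site that worked from the Part 2 visit list would draw blood at each visit and not request ALT or bilirubin. A rise without symptoms could then go unnoticed, and the liver findings from the extension would rest on irregular testing.

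**Working it through.** No power or sample size figure bears on this point, so the check compares the sections and then counts visits.

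**1. Where CMP is timed.**

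| Period | Section 3.1 text | Appendix 1 table |
|---|---|---|
| Part 1 | screening, enrolment, every 2 weeks to week 8 | 6 of 6 columns marked |
| Part 2 | not in the each-visit list; not in any 6- to 48-month entry | row present, 0 of 8 columns marked |
| Post-study | every 2 weeks to week 4 | 2 of 4 columns marked (weeks 1 and 3) |

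**2. Whether the blank Part 2 row is informative.** All five laboratory rows of that table are blank, so the CMP row has to be read beside the others.

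| Part 2 row in Appendix 1 | Columns marked | Timing given in Section 3.1 |
|---|---|---|
| CBC | 0 of 8 | each visit |
| Reticulocyte | 0 of 8 | each visit |
| Platelet reticulocyte | 0 of 8 | each visit |
| Peripheral smear | 0 of 8 | each visit, if indicated |
| CMP | 0 of 8 | none |

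A blank row therefore does not mean that a test is not done. But for the other four rows Section 3.1 supplies the timing, and for CMP it does not. The reverse case is the two-weekly Part 1 list in Section 3.1, which leaves out CBC: there Appendix 1 fills the gap by marking CBC at every Part 1 visit. Part 2 CMP is the only one of the laboratory rows whose timing appears in neither place.

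**3. What the liver rules need.** Criterion 1 needs ALT with bilirubin (or ALT with INR). Criterion 2 needs ALT alone, criterion 3 ALT with symptoms, criterion 4 a persistent ALT elevation, and criterion 5 an ALT elevation that cannot be followed weekly. That is ALT in 5 of 5. The weekly repeat testing in Sections 6.4.1 and 6.4.6.2 starts only once an ALT elevation is known.

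**4. Visits affected.** Section 3.1 allows visits every 4 weeks, then every 8 weeks at the investigator's discretion, and does not say when the change occurs. All-8-weekly and all-4-weekly schedules therefore bound the count. With about 52.2 weeks in a year:

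- 48 months: 4 × 52.2 ≈ 209 weeks. 209 / 8 ≈ 26 visits; 209 / 4 ≈ 52 visits.
- 18 months: 1.5 × 52.2 ≈ 78 weeks. 78 / 8 ≈ 10 visits; 78 / 4 ≈ 20 visits.

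The 48-month length is supported by the Part 2 heading, the Section 3.1 schedule and Appendix 1; the 18-month length stands only in Section 1.2.

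**The case against.** The strongest reply is that CMP was plainly meant to be done. Section 3.1 names Appendix 1 as the schedule of events, and Appendix 1 lists CMP for Part 2 in the same block as the tests done at every visit. Its columns are six-month milestones, not the 4- to 8-week visits, so blank cells may just mark the per-visit tests, or an entry spanning the row may have been lost when the PDF was read. The Section 3.1 lists are also demonstrably loose, since one omits the CBC on which the primary endpoint rests. This stands as evidence of intent. It does not supply a timing, because the list that gives the per-visit tests is running text and names every test in the block except CMP.

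Nor is the timing supplied elsewhere. The reference to the package insert is attached to platelet-count dose handling. The blood-volume table in Section 5.7 names no tests. The algorithm cited in Section 8.3.1.2 is not among the two appendices in the table of contents.

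Three stronger readings are tempting, and the documents do not support them:

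- A reader might infer that the stopping criteria can never be met in Part 2. Section 3.1 lets the investigator call for extra monitoring, and symptoms could prompt a test. Placebo subjects who cross over also follow the Part 1 schedule, including its CMP, for their first 8 weeks.
- A reader might infer that a liver-injury rate from the extension will be too low. Section 8.3.1.2 plans no such rate; it speaks of monitoring, and of continuing or stopping drug.
- A reader might use the interim statement that "only one patient was removed because of a study drug related event (elevated LFTs") to size the problem. That removal is not attributed to Part 2, and it shows that liver tests were being done, so it does not measure missed tests.

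**Conclusion.** The point holds as an inconsistency with a safety consequence. The Part 2 visit list omits the panel that yields ALT and bilirubin, no section gives it a timing in Part 2, and Appendix 1, the safety review, the safety analysis section and all five stopping criteria presuppose it. Followed literally, the list leaves symptomless elevations to discretionary or symptom-prompted testing over about 26 to 52 visits (48 months) or 10 to 20 visits (18 months). These counts assume a subject who stays for the full period, and they overstate the gap for placebo crossovers if their 8 open-label weeks are counted within Part 2. The conclusion also assumes that no schedule is given in the algorithm cited in Section 8.3.1.2, which could not be checked. It does not rest on the blank Appendix 1 row alone, and it does not say that liver chemistry was left out in practice.

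**What to change.** Reconcile three places: the Part 2 list in Section 3.1, the Part 2 CMP row in Appendix 1, and the liver criteria in Sections 6.4.1 and 6.4.6.2. After the change, the tests on which the criteria depend should appear in the Part 2 list with a stated timing, and the Appendix 1 row should show the same timing. The clinical team sets the frequency. In the same edit, settle whether Part 2 lasts 48 or 18 months, and either attach the algorithm cited in Section 8.3.1.2 or replace the reference with one to Section 6.4.1.

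The cost is a protocol wording amendment plus laboratory work at visits where blood is already drawn for the CBC. The documents give no cost for the assay. Sample size, randomization and the primary analysis are unaffected.
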